9.2.3 Treatment-Emergent Adverse Events by SOC and PT

Treatment-emergent adverse events will be summarized by SOC and PT; by maximum relationship to study drug as assessed by the investigator (e.g., reasonable possibility or no reasonable possibility) and SOC and PT; by maximum severity and SOC and PT; and by subject number and SOC and PT. Specific adverse events will be counted once for each subject for calculating percentages, unless stated otherwise. In addition, if the same adverse event occurs multiple times within a subject, the highest severity and level of relationship to investigational product will be reported.

In addition, treatment-emergent adverse events will be summarized by PT and sorted by decreasing frequency for the elagolix plus E2/NETA group.

In addition, for subjects who received elagolix 200 mg BID alone at Study Day 1, TEAEs during the placebo-controlled Treatment Period will be summarized separately for the first 6-month and second 6-month by SOC and PT.

9.2.4 Treatment-Emergent Adverse Events per Patient-Years of Exposure

An overview of AEs for All Elagolix plus E2/NETA Analysis Set will be presented per 100 patient-years. In addition, TEAEs for All Elagolix plus E2/NETA Analysis Set will be presented per 100 patient-years by SOC and PT. AEs per 100 patient-years of exposure are defined as the number of AEs divided by the total exposure in 100 patient-years. Note that one event per preferred term per day per subject will be counted in the calculation of the number of AEs (i.e., a preferred term will not be counted twice on the same day for the same subject).

$$\text{TEAEs per 100 patient-years of exposure} = 100 \times \frac{\text{Number of TEAEs}}{\text{Total Patient Years}}$$

where total patient years are defined as the sum of the study drug exposure (defined as date of last dose of elagolix plus E2/NETA – date of first dose of elagolix plus E2/NETA + 30 days) of all subjects normalized by 365.25, and rounded to one decimal place.

9.2.5 Serious Adverse Events (Including Deaths) and Adverse Events Leading to Study Drug Discontinuation

The number and percentage of subjects experiencing the following categories will be tabulated according to the primary MedDRA SOC and PT. In addition, listing of subjects experiencing the following categories will be generated.

- Treatment-emergent SAEs

- Treatment-emergent AEs leading to discontinuation of study drug
- Treatment-emergent AEs leading to death

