6.1.4 Adverse Event Collection Period

All adverse events reported from the time of study drug administration until 30 days following discontinuation of study drug administration have elapsed will be collected, whether solicited or spontaneously reported by the subject. All nonserious adverse events of bone fracture, clinically significant BMD loss, or newly diagnosed medically-related bone condition will be collected during the Follow-Up Period, until the subject discontinues from study participation. In addition, serious adverse events and protocol-related nonserious adverse events will be collected from the time the subject signed the study-specific informed consent.

Adverse event information will be collected as shown in Figure 2.

SAEs and Nonserious AEs SAEs and Elicited and/or Spontaneously Protocol-Related Reported Nonserious AEs SAEs and Bone-related AEs End of Study Consent Study Drug Study 30 days After (end of Signed Stopped Drug Start Study Drug Follow-Up) Stopped

Figure 2. Adverse Event Collection

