2.5 End of 12-Month Placebo-Controlled Treatment Period Analysis

An end-of-placebo-controlled treatment period analysis of the primary, secondary and other efficacy variables along with demographic and safety variables will be performed after the last subject completes the 12-Month placebo-controlled Treatment Period. These analyses will include data collected during the Treatment Period (placebo-controlled and open-label Treatment Periods) and the Follow-Up Period up to the data cut-off for the interim lock. The database will be versioned for an interim soft lock and any discrepant data will be clarified before the versioning. Analyses will be performed by AbbVie.

Since this end-of-placebo-controlled treatment period analysis is the only and final analysis of the primary and key secondary endpoints, no additional adjustment of alpha-level is necessary.

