2.6 Treatment Month 24 and Month 36 Analyses

At the end of Treatment Month 24 and Month 36, analysis of the efficacy and safety variables may be performed after the last subject completes the Treatment Month 24 and Month 36 visit, respectively. For subjects who prematurely discontinued during the treatment period, their data collected during the Follow-up Period will be included in the analysis, as appropriate. The database will be versioned for an interim lock and any discrepant data will be clarified before the versioning. Analyses will be performed by AbbVie.

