9.2.1 Treatment-Emergent Adverse Events

Treatment-emergent adverse events (TEAEs) for each safety population are defined as follows:

TEAEs during the 12-month placebo-controlled Treatment Period on Safety Analysis Set during the placebo-controlled Treatment Period

TEAEs during the 12-month placebo-controlled Treatment Period are defined as any AEs with the onset that is on or after the first dose of study drug during the 12-month placebo-controlled Treatment Period and no more than 30 days after the last dose of study drug for subjects who premature discontinue during the 12-month double-blind Treatment Period or until the first dose of study drug in the open-label Treatment Period for subjects who enter the open-label Treatment Period. AEs starting more than 30 days following discontinuation of study drug will not be included in summaries of treatment-emergent AEs but will be summarized separately.

TEAEs during the open-label Treatment Period on the Safety Analysis Set during the open-label Treatment Period

TEAEs during the open-label Treatment Period are defined as any AEs with the onset that is on or after the first dose of study drug during the open-label Treatment Period and no more than 30 days after the last dose of study drug in the study. AEs starting more than 30 days following discontinuation of study drug will not be included in summaries of treatment-emergent AEs but will be summarized separately.

TEAEs for All Elagolix plus E2/NETA Analysis Set

TEAEs for All Elagolix plus E2/NETA Analysis Set are defined as any AEs with the onset that is on or after the first dose of elagolix plus E2/NETA (either in the placebo-controlled Treatment Period or open-label Treatment Period) and no more than 30 days after last dose of elagolix plus E2/NETA. AEs starting more than 30 days following discontinuation of study drug will not be included in summaries of treatment-emergent AEs but will be summarized separately.

The number and percentage of subjects experiencing treatment-emergent AEs will be summarized overall, as well as by primary MedDRA SOC and PT by treatment group.

The SOC's will be presented in alphabetical order, and the PT's will be presented in alphabetical order within each SOC.

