9.5.8 Pregnancy Results

Pregnancies and outcomes will be summarized by treatment group for the Treatment Period (placebo-controlled and open-label) and Follow-up Period. Subjects with

conception date by sponsor more than 30 days after the last dose of study drug will be included in the summaries for the Follow-up Period.

Listings will be prepared of all pregnancy test results for any subject who ever had a positive pregnancy test at any time point during the study.

Positive pregnancy test results (serum, urine, and both) and a listing of all positive pregnancy test results will be provided.

Pregnancy outcome will be summarized by treatment group. Additionally, a listing of pregnancy information will be provided. Pregnancy outcome includes:

- Number of pregnancies
- Live births
 - Pre-term (extremely pre-term: < 28 weeks; very pre-term: 28 - < 32 weeks; moderate to late preterm: 32 - < 37 weeks)
 - Term (37 - < 42 weeks)
 - Post-term (\geq 42 weeks)
- Spontaneous abortion (< 6, 6 - 13, > 13 weeks gestation)
- Termination of pregnancy
- Ectopic pregnancy
- Still birth
- Congenital anomaly
- Lost to follow-up
- Subjects refused to provide information
- Other
- Ongoing (pregnancy ongoing at end of study)
- Maternal exposure to Elagolix/Study drug (0, > 0 - 4, > 4 - 6, > 6 - 12, > 12 - 23, > 23 weeks)
- Embryo/Fetal exposure to Elagolix/Study drug assessed by the sponsor (0, > 0 - 4, > 4 - 6, > 6 - 12, > 12 weeks)

Annualized pregnancy rate during treatment will be reported by treatment group. The annualized pregnancy rate will be calculated as

$$\text{Annualized pregnancy rate} = (\text{number of pregnancies/days of exposure to treatment}) \times 365$$

In addition, listings of fetal/newborn, infant post-delivery assessments, and infant during 6 – 12 month follow-up assessment will be provided.

The above information will be summarized primarily based on data collected on the pregnancy case report form. Information not directly obtained from the case report form will use the following definitions.

Gestation day

Gestation Day 0 was calculated by subtracting the gestational age provided according to the first trimester ultrasound date from the first trimester ultrasound date. If no gestational age was provided, it will be imputed by subtracting 14 days from the midpoint between the subject's last negative pregnancy test date and the date of the positive pregnancy test.

Gestational age

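### Adverse-event patient-years add 30 days after the last dose without stopping at the data cut-off, so rates at interim locks can be slightly too low

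*SAP*

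**What the plan says.** SAP 9.2.4 reports adverse events per 100 patient-years for the All Elagolix plus E2/NETA Analysis Set. Total patient-years sum each woman's last combination dose date minus the "date of first dose of elagolix plus E2/NETA + 30 days) of all subjects normalized by 365.25". There is no separate rule for women still dosing.

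The numerator is defined in SAP 9.2.1. For this set, an event counts if its onset is on or after the first combination dose and "no more than 30 days after last dose of elagolix plus E2/NETA". Protocol 6.1.4 collects adverse events over the same tail, "until 30 days following discontinuation of study drug administration have elapsed".

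The analysis is run while women are still on treatment. SAP 2.5 places the main analysis after the last subject completes Month 12 of a 48-month Treatment Period. It includes open-label data and data from the "Follow-Up Period up to the data cut-off for the interim lock". SAP 2.6 adds analyses that "may be performed after the last subject completes the Treatment Month 24 and Month 36 visit".

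SAP 9.5.8 gives a second rate, annualized pregnancies during treatment, calculated as "number of pregnancies/days of exposure to treatment" times 365. The same section says that subjects with a "conception date by sponsor more than 30 days after the last dose of study drug will be included in the summaries" for the Follow-up Period.

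**The concern.** A rate per patient-year is interpretable only if the denominator holds time in which an event could have been recorded. At an interim lock, a woman whose latest dose is at the cut-off has no observed 30-day tail. SAP 9.2.4 credits her with one anyway. The error has one direction: it adds time and no events, so it lowers the rate. It reaches every rate in the section, both the overview and the tables by system organ class and preferred term. It is largest for women who started the combination recently. These include women randomized to placebo, who join the set at their first open-label combination dose (SAP 4.0).

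The pregnancy rate raises a related question. Only conceptions more than 30 days after the last dose are assigned to Follow-up, so earlier ones may belong to the Treatment Period. Whether they enter the rate, and over what time, is not stated.

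**Working it through.** The plan states no numerical rate, so there is no figure to reproduce. The check is on person-time.

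**One woman.** Let T = last dose − first dose + 1, in days on the combination (a month is 28 days, Protocol 1.3).

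- SAP 9.2.4 denominator: (T − 1) + 30 = T + 29.
- Treatment-emergent window if she has stopped: T + 30. At T = 336 this compares 365 with 366 days, a difference of −0.3%.
- Observed time if she is still dosing and her last dose is at the cut-off: T. The excess is 29 days, and the rate is multiplied by T/(T + 29).

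| T (days) | T/(T + 29) | Rate error |
|---|---|---|
| 28 | 28/57 | −50.9% |
| 336 | 336/365 | −7.9% |
| 672 | 672/701 | −4.1% |
| 1008 | 1008/1037 | −2.8% |

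**Whole analysis set.** Inputs from the documents: 400, 100 and 200 women randomized, starting the combination at day 0, day 168 and day 336 respectively. Assumptions: 0 to 60% drop out, all at half the lock time; ongoing women have 0 to 336 further days on drug at the cut-off; their last dose is at the cut-off.

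Largest effect at the Month 12 lock (no dropout, no extra days):

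- Observed: 400 × 336 + 100 × 168 = 151,200 days = 414.0 patient-years.
- SAP formula: 151,200 + 500 × 29 = 165,700 days = 453.7 patient-years.
- Rate ratio: 151,200/165,700 = 0.912, i.e. −8.8%.

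Smallest effect at the Month 12 lock (60% dropout at day 168, 336 extra days):

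- Observed, ongoing women: 160 × 672 + 40 × 504 + 80 × 336 = 154,560 days.
- Observed, stopped women: 240 × (168 + 30) = 47,520 days. The dropouts from the other two arms have no combination time.
- Total: 202,080 days = 553.3 patient-years.
- SAP formula: 202,080 + 280 × 29 − 240 × 1 = 209,960 days = 574.8 patient-years.
- Rate ratio: 202,080/209,960 = 0.962, i.e. −3.8%.

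| Lock | Rate understated by |
|---|---|
| Month 12 | 3.8 to 8.8% |
| Month 24 | 2.2 to 5.0% |
| Month 36 | 1.5 to 3.2% |
| All finished | about 0 |

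**Sensitivity to the last-dose date.** If the last recorded dose is 28 days before the cut-off, the denominator is (T − 28 − 1) + 30 = T + 1. At T = 336 that is 337/336, an excess of 0.3%, and less at longer T.

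**Pregnancy rate (conditional).** Suppose exposure means last dose − first dose + 1 and conceptions in the 30-day tail are counted. For a woman who has stopped, the rate would then be too high by 30/T: 8.9% at 336 days and 4.5% at 672 days. In the placebo-controlled period, women who roll over have no off-drug tail. With a fraction d dropping out at day D, the group figure is 30d/[336(1 − d) + dD]. For d = 10 to 40% and D = 84 or 168 (assumed), this is 0.9 to 5.1%.

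**The case against.** The 30 days are there for a good reason. They match the numerator window and the protocol's collection period, so for women who have stopped the formula is right to within a day. A reader might infer that the adverse-event rate as a whole counts events and time over different periods. The documents do not support that: the mismatch is confined to women still dosing at an interim lock.

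The size is also a ceiling. The SAP gives no last-dose rule for ongoing women. Open-label dose dates are recorded at on-site and phone visits (Protocol 5.5.6), which are monthly, so the last recorded dose may precede the cut-off by up to about a month and absorb nearly all the excess. This stands, although it leaves the answer to an unstated data convention.

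A reader might also infer that the dilution favours the drug over placebo. Every woman in this set has received the combination, and SAP 9.1 plans no comparison in it unless otherwise specified. The tables of numbers and percentages of subjects do not use this denominator.

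Finally, it is tempting to say that the pregnancy rate is inflated. SAP 9.5.8 does not establish this. It describes the rate as during treatment, never says that its numerator includes conceptions in the 30-day tail, and leaves exposure days undefined. SAP 6.0 and the maternal-exposure definition in 9.5.8 point to last minus first plus 1. SAP 9.2.4, however, applies the term study drug exposure to a quantity that includes the 30 days; on that definition the mismatch would largely disappear.

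**Conclusion.** The adverse-event point holds in limited form. SAP 9.2.4 states a rule for all subjects and no other section truncates it. At locks taken while women are still dosing, up to 29 days per ongoing woman can enter the denominator with no possible events. Rates pooled over the set are understated by at most about 4 to 9% at Month 12, 2 to 5% at Month 24 and 1.5 to 3% at Month 36. These ranges rest on the dropout, extra-time and last-dose assumptions above. They fall to near zero with a last recorded dose about 28 days before the cut-off, or once all women have finished. The outputs are descriptive: alpha, power and the efficacy analyses are untouched.

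The pregnancy rate needs a definition. An error has not been shown.

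**What to change.** In SAP 9.2.4, define time at risk as min(last combination dose + 30 days, data cut-off, end of observation) − first combination dose + 1. State that for ongoing women the end date is the cut-off or last contact. This needs no new data; the downside is slightly higher adverse-event rates at interim locks.

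In SAP 9.5.8, define the exposure days and the conceptions that count on one window. The simplest choice is conceptions on or before the last dose, over last dose − first dose + 1. If the 30-day tail is kept, extend the denominator to match, and also end time at the data cut-off, at the start of the next treatment period and at conception. Otherwise a placebo woman who rolls over could have open-label days counted as placebo time.

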9.2.6 Adverse Events of Special Interest

Adverse events of special interest will be summarized by SOC and PT and will be based on standardized or company MedDRA queries (SMQs or CMQs), or based on adjudication results.

Detailed information about the search criteria are provided in [Appendix B](#).

9.2.7 Hot Flashes and Night Sweats

Summary of total number of hot flashes and night sweats in the last 24 hours by subject-reported severity categories and summary of total number of hot flashes, night sweats, and hot flashes or night sweats in the last 24 hours by maximum subject-reported severity will be provided by treatment group at each time point during the Treatment Period and Follow-up Period. Listings of subject IDs associated with hot flush and night sweats in the last 24 hours by subject-reported severity categories and by maximum subject-reported severity categories will be provided separately.

In addition, summary of time to first onset of treatment-emergent AE of hot flush, night sweats, hot flush and/or night sweats will be provided separately.

9.2.8 Post-Treatment Adverse Events

Post-Treatment Adverse Events are defined as AEs starting more than 30 days following discontinuation of study drug in the Treatment Period. The Post-Treatment AEs will be summarized as follows:

- Overview of Post-Treatment AEs
- Post-Treatment AEs by SOC and PT
- Post-Treatment SAEs by SOC and PT

In addition, listing of subjects with Post-Treatment AEs by SOC and PT and Post-Treatment SAEs by SOC and PT will be provided.

9.3 Analysis of Laboratory Data

Data collected from central and local laboratories, including additional laboratory testing due to an SAE, will be used in all analyses, except for Baseline where SAE-related laboratory assessments on or before the first dose of study drug will be excluded. The clinical laboratory tests defined in the protocol operations manual (i.e., hematology and clinical chemistry) will be summarized.

Each laboratory variable will be summarized for all time points (starting with Baseline) with the number of non-missing observations, mean and standard deviation, median, minimum and maximum. Mean change from baseline to each applicable post-baseline visit will be summarized for selected laboratory variables, with the number of observations, baseline mean, and visit mean. The change from baseline mean, standard error, and 95% confidence interval will be presented for the mean change from baseline within each treatment group and difference between each elagolix group and placebo. Selected laboratory variables are lipid variables, liver variables (alkaline phosphatase, ALT, AST, bilirubin), hemoglobin, hematocrit, platelet count, and red blood cell (RBC) count. For lipid variables, in addition to low-density lipoprotein cholesterol (LDL-C), high-density lipoprotein cholesterol (HDL-C), total cholesterol, triglycerides (TG) and apolipoprotein A and B, the following ratios will be included: the ratio of total cholesterol to HDL-C, the ratio of LDL-C to HDL-C, the ratio of TG to HDL-C, and the ratio of non-HDL-C (calculated as total cholesterol minus HDL-C) to HDL-C.

Changes in selected laboratory parameters will be tabulated using shift tables by NCI CTC criteria and categorized as low, normal, or high based on the normal ranges of the laboratory used for each sample. A shift table from baseline either to the worse value (based on NCI CTC criteria) during treatment or to minimum and maximum value (based on normal range), will be created. A similar shift table will be provided to summarize shifts from baseline to the final post-baseline value.

Laboratory abnormalities meeting CTC criteria grade 3 or 4 will be summarized.

The number and percentage of subjects meeting the following sponsor-defined potentially clinically significant lipid values will be summarized at baseline and each relevant visit by treatment group in the appropriate Treatment Period:

- Total cholesterol: ≤ 300 , $> 300 - \leq 400$, $> 400 - \leq 500$, and > 500 mg/dL
- HDL-C: < 40 and ≥ 40 mg/dL
- LDL-C: < 130 , $\geq 130 - < 160$, $\geq 160 - < 190$, and ≥ 190 mg/dL
- TG: ≤ 150 , $> 150 - \leq 300$, $> 300 - \leq 500$, $> 500 - \leq 1000$, and > 1000 mg/dL
- LDL-C/HDL-C ratio: ≤ 3 , and > 3
- Total cholesterol/HDL-C ratio: ≤ 4.5 , and > 4.5

In addition, the number and percentage of subjects who have potentially clinically significant (PCS) lipid values meeting the following criteria any time during the appropriate Treatment Period will be summarized by treatment group. Listings will be provided to summarize subject-level laboratory data for subjects meeting PCS criteria.

- Total cholesterol > 200 mg/dL
- LDL-C > 130 mg/dL
- LDL-C > 160 mg/dL
- HDL-C < 40 mg/dL
- TG > 150 mg/dL
- TG/HDL-C ratio > 3.5
- LDL-C/HDL-C ratio > 4

The following plots will be provided by treatment group for HDL-C, LDL-C, and triglycerides during the appropriate Treatment Period:

- Final post-baseline lab values vs. Baseline lab values
- Final post-baseline lab values vs. Baseline lab values for subjects with NCI CTC Grade 3 or 4

- Worst post-baseline lab values vs. Baseline lab values
- Worst post-baseline lab values vs. Baseline lab values for subjects with NCI CTC Grade 3 or 4
- Mean percent change from baseline in lipid parameters over time

In addition, plots of mean lab values over time during the Treatment Period will be provided for hemoglobin, total cholesterol, HDL-C, LDL-C, triglycerides, LDL-C/HDL-C ratio, ALT, AST, bilirubin, apolipoprotein A and apolipoprotein B.

The number and percentage of subjects in each treatment group with maximum on-treatment laboratory values meeting the following criteria compared to the upper limit of normal (ULN) during the appropriate Treatment Period will be summarized to assess potential hepatotoxicity.

- $ALT \geq 3 \times ULN$ and total bilirubin $\geq 2 \times ULN$
- $AST \geq 3 \times ULN$ and total bilirubin $\geq 2 \times ULN$
- ALT and $AST \geq 3 \times ULN$ and total bilirubin $\geq 2 \times ULN$
- $ALT \geq 3 \times ULN$ and total bilirubin $< 2 \times ULN$
- $AST \geq 3 \times ULN$ and total bilirubin $< 2 \times ULN$
- ALT and $AST \geq 3 \times ULN$ and total bilirubin $< 2 \times ULN$
- $ALT \geq 3 \times ULN$ and total bilirubin $\geq 1.5 \times ULN$
- $AST \geq 3 \times ULN$ and total bilirubin $\geq 1.5 \times ULN$
- ALT and $AST \geq 3 \times ULN$ and total bilirubin $\geq 1.5 \times ULN$
- $ALT \geq 3 \times ULN, \geq 5 \times ULN, \geq 10 \times ULN, \geq 20 \times ULN$
- $AST \geq 3 \times ULN, \geq 5 \times ULN, \geq 10 \times ULN, \geq 20 \times ULN$
- Total bilirubin $\geq 1.5 \times ULN, \geq 2.0 \times ULN$

The maximum ratio relative to the ULN is used to determine if subjects met the criteria listed above. The ALT, AST, and total bilirubin values do not need to be concurrent in order to meet the defined criteria. For ALT, AST, and total bilirubin, a subject is counted if the post-baseline laboratory value during the Treatment Period meets the above criteria

regardless of Baseline laboratory value (i.e., the post-baseline laboratory value does not need to be worse than Baseline laboratory value).

A listing of all ALT, AST, total bilirubin, and alkaline phosphatase values will be provided for each subject who meets any of the criteria defined above.

The following plots will be generated: peak AST vs. peak bilirubin; peak ALT vs. peak bilirubin.

